6.4 Investigator Reporting Responsibilities

The conduct of the study will comply with all FDA safety reporting requirements.

IND Annual Reports

If the FDA has granted an IND number, it is a requirement of 21 CFR 312.33, that an annual report is provided to the FDA within 60-days of the IND anniversary date. 21 CFR 312.33

provides the data elements that are to be submitted in the report. The Annual Report should be filed in the study's Regulatory Binder, and a copy provided to Celgene Corporation and Novartis Pharmaceuticals as supporters of this study as follows.

Celgene Corporation

Attn: Medical Affairs Operations
[name]
[name]
[name]
[contact]

And

CS&E Department
Novartis Pharmaceuticals Corporation
[name]
[name]
[contact]

All adverse experience reports must include the patient number, age, sex, weight, severity of reaction (i.e. mild, moderate, severe), relationship to drug (i.e. probably related, unknown relationship, definitely not related), date and time of administration of test medications and all concomitant medications, and medical treatment provided. The investigator is responsible for evaluating all adverse events to determine whether criteria for “serious” and as defined above are present. The investigator is responsible for reporting adverse events to Celgene as described below.

6.4.1 Expedited reporting by investigator to Celgene

Serious adverse events (SAE) are defined above. The investigator must inform the study supporters, Novartis Pharmaceuticals and Celgene in writing using a Celgene SAE form or MEDWATCH 3500A form of any SAE within 24 hours of being aware of the event. The written report must be completed and supplied to Celgene by facsimile within 24 hours/1 business day. The initial report must be as complete as possible, including an assessment of the causal relationship between the event and the investigational product(s) if available. Information not available at the time of the initial report (e.g., an end date for the adverse event or laboratory values received after the report) must be documented on a follow-up report. A final report to document resolution of the SAE is required. The Celgene tracking number (RV-ST-PI-0558) and the institutional protocol number should be included on SAE reports (or on the fax cover letter) sent to Celgene. A copy of the fax transmission confirmation of the SAE report to Celgene should be attached to the SAE and retained with the patient records.

6.4.2 Report of Adverse Events to the Institutional Review Board

The principal Investigator is required to notify his/her Institutional Review Board (IRB) of a serious adverse event according to institutional policy.

6.4.3 Investigator Reporting to the FDA

Serious adverse events (SAEs) that are **unlisted/unexpected, and at least possibly associated to the drug**, and that have not previously been reported in the Investigators brochure, or reference safety information document should be reported promptly to the Food and Drug Administration (FDA) by telephone or by fax. Fatal or life threatening SAEs that meet the criteria for reporting to the FDA must be reported to the FDA within 7 calendar days after awareness of the event. All other SAEs that meet the criteria for reporting to the FDA must be reported to the FDA within 15 calendar days after awareness of the event. A clear description of the suspected reaction should be provided along with an assessment as to whether the event is **drug or disease related**. In accordance with 21CFR312.32, adverse events associated with the use of investigational use will be reported to the FDA. The PI is responsible for notifying the FDA and all other participating investigators in a written IND safety report of any AE that is both serious and unexpected.

6.5 Adverse Event Updates/IND Safety Reports

Celgene shall notify the Investigator via an IND Safety Report of the following information:

- Any AE associated with the use of drug in this study or in other studies that is both serious and unexpected.
- Any finding from tests in laboratory animals that suggests a significant risk for human subjects including reports of mutagenicity, teratogenicity, or carcinogenicity.

The Investigator shall notify his/her IRB/EC promptly of these new serious and unexpected AE(s) or significant risks to subjects.

The Investigator must keep copies of all AE information, including correspondence with Celgene and the IRB/EC, on file (see Section 11.4 for records retention information).

7 Response Criteria

Baseline lesion assessments must occur within ≤ 28 days of protocol therapy initiation or as indicated in Section 2, Schedule of Study Assessments.

Efficacy assessments are scheduled to occur after every 2 cycles of protocol therapy or approximately every 8 weeks (as detailed in Schedule of Study Assessments Table). All partial and complete responses will be confirmed with another efficacy assessment in no less than 4 weeks apart.

Measurement of Effect

Measurable Disease - the presence of at least one measurable lesion at baseline is only mandatory for the expansion cohort. If the measurable disease is restricted to a solitary lesion, its neoplastic nature should be confirmed by cytology/histology.

Measurable Lesions - lesions that can be accurately measured in at least one dimension with longest diameter ≥ 20 mm using conventional techniques or ≥ 10 mm with spiral CT scan.

Non-measurable Lesions - all other lesions, including small lesions (longest diameter < 20 mm with conventional techniques or < 10 mm with spiral CT scan), i.e., bone lesions, leptomeningeal disease, ascites, pleural/pericardial effusion, inflammatory breast disease, lymphangitis cutis/pulmonis, cystic lesions, and also abdominal masses that are not confirmed and followed by imaging techniques; and:

All measurements should be taken and recorded in metric notation, using a ruler or calipers. All baseline evaluations should be performed as closely as possible to the beginning of treatment and never more than 4 weeks before the beginning of the treatment. The same method of assessment and the same technique should be used to characterize each identified and reported lesion at baseline and during follow-up. Clinical lesions will only be considered measurable when they are superficial (e.g., skin nodules and palpable lymph nodes). For the case of skin lesions, documentation by color photography, including a ruler to estimate the size of the lesion, is recommended.

7.1.1 Methods of Measurement

- CT and MRI are the best currently available and reproducible methods to measure target lesions selected for response assessment. Conventional CT and MRI should be performed with cuts of 10 mm or less in slice thickness contiguously. Spiral CT should be performed using a 5 mm contiguous reconstruction algorithm. This applies to tumors of the chest, abdomen and pelvis. Head and neck tumors and those of extremities usually require specific protocols.
- Lesions on chest X-ray are acceptable as measurable lesions when they are clearly defined and surrounded by aerated lung. However, CT is preferable.
- Tumor markers alone cannot be used to assess response. If markers are initially above the upper normal limit, they must normalize for a patient to be considered in complete clinical response when all lesions have disappeared.
- Cytology and histology can be used to differentiate between PR and CR in rare cases (e.g., after treatment to differentiate between residual benign lesions and residual malignant lesions in tumor types such as germ cell tumors).

Baseline Documentation of “Target” and “Non-Target” Lesions

- All measurable lesions up to a maximum of five lesions per organ and 10 lesions in total, representative of all involved organs should be identified as target lesions and recorded and measured at baseline.
- Target lesions should be selected on the basis of their size (lesions with the longest diameter) and their suitability for accurate repeated measurements (either by imaging techniques or clinically).

- A sum of the longest diameter (LD) for all target lesions will be calculated and reported as the baseline sum LD. The baseline sum LD will be used as reference by which to characterize the objective tumor response.
- All other lesions (or sites of disease) should be identified as non-target lesions and should also be recorded at baseline. Measurements of these lesions are not required, but the presence or absence of each should be noted throughout follow-up.

7.1.2 Response Criteria

Evaluation of Target Lesions

Complete Response (CR)	Disappearance of all target lesions
Partial Response (PR)	At least a 30% decrease in the sum of the LD of target lesions, taking as reference the baseline sum LD
Progressive Disease (PD)	At least a 20% increase in the sum of the LD of target lesions, taking as reference the smallest sum LD recorded since the treatment started or the appearance of one or more new lesions
Stable Disease (SD)	Neither sufficient shrinkage to qualify for PR nor sufficient increase to qualify for PD, taking as reference the smallest sum LD since the treatment started

Evaluation of Non Target Lesions

Complete Response (CR)	Disappearance of all non-target lesions and normalization of tumor marker level
Incomplete Response/ Stable Disease (SD):	Persistence of one or more non-target lesion(s) or/and maintenance of tumor marker level above the normal limits
Progressive Disease (PD)	Appearance of one or more new lesions and/or unequivocal progression of existing non-target lesions

7.1.3 Confirmation

The main goal of confirmation of objective response is to avoid overestimating the response rate observed. In cases where confirmation of response is not feasible, it should be made clear when reporting the outcome of such studies that the responses are not confirmed.

To be assigned a status of PR or CR, changes in tumor measurements must be confirmed by repeat assessments that should be performed no less than 4 weeks after the criteria for response are first met. Longer intervals as determined by the study protocol may also be appropriate.

In the case of SD, follow-up measurements must have met the SD criteria at least once after study entry at a minimum interval (in general, not less than 6-8 weeks) that is defined in the study protocol

8 Protocol Amendments/Deviations

8.1 Protocol amendments

Any amendment to this protocol must be agreed to by the Principal Investigator and reviewed by Celgene. Amendments should only be submitted to IRB/EC after consideration of Celgene review. Written verification of IRB/EC approval will be obtained before any amendment is implemented.

8.2 Protocol deviations

When an emergency occurs that requires a deviation from the protocol for a subject, a deviation will be made only for that subject. A decision will be made as soon as possible to determine whether or not the subject (for whom the deviation from protocol was effected) is to continue in the study. The subject's medical records will completely describe the deviation from the protocol and state the reasons for such deviation. In addition, the Investigator will notify the IRB/EC in writing of such deviation from protocol.

Non-emergency minor deviations from the protocol will be permitted with approval of the Principal Investigator.

9 Data Management

9.1 Analyses and Reporting

Data will be analyzed and reported within 3 months of enrolment of the last patient in the expansion cohort. All subsequent data collected will be analyzed and reported in a follow-up clinical report.

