 - Inability to re-treat patient within 2 wks of scheduled treatment due to treatment-related adverse event
 - Inability to deliver all doses of Lenalidomide and or Everolimus during the first cycle due to an unexpected drug-related toxicity (if toxicity is an

expected toxicity as per current package insert, then it will not be considered a DLT). These subjects should be discontinued from the study

In the event of study discontinuation prior to completing the entire first treatment cycle for reasons other than DLT, the affected subject will be considered inevaluable for toxicity and will be replaced by another subject to be treated at the same dose-level.

Secondary:

- Significant drug-drug interaction will be determined through pharmacokinetic analysis for parent drug and metabolites (the following PK parameters will be estimated and reported for each agent according to dose level – (AUC_{0→t}) Area under the concentration-time curve from the time of dosing to the time of the last observation; (AUC_{0→∞}) Area under the concentration-time curve from the time of dosing extrapolated to infinity; (C_{max}) Maximum serum concentration observed postdose; (T_{max}) Time point at which the C_{max} occurs; (t_{1/2}) Elimination half-life, determined as 0.693/λ_z)
- The frequency of achieving a complete plus partial response to the 2 drug combination by dose cohort. Response will be assessed by cross sectional imaging after every 2 cycles and will be categorized according to RECIST 1.1 criteria.

Correlative:

- Mean change in immunological biomarkers at baseline, after 1 cycle of protocol directed therapy and at disease progression by dose cohort
- Mean change in plasma levels of inflammatory markers at baseline, after 1 completed cycle of therapy and at disease progression
- Plasma level of cathepsin G at baseline, after 1 cycle of therapy and following the first diagnosis of venous thromboembolic disease

STUDY DURATION: 18-24 months	TOTAL SAMPLE SIZE: 45

DOSING REGIMEN(S):
 
According to dose cohort:
 
Lenalidomide once daily days 1-28 of a 28 day cycle
 
Everolimus once daily continuously (day 1-28)
	
DRUG SUPPLIES:
 
For study participants, Celgene Corporation will provide lenalidomide at no charge through the RevAssist® program.
 
Everolimus will be supplied by Novartis Pharmaceuticals Corporation and dispensed through the Investigational Drug Pharmacy

2 Schedule of Study Assessments *

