Procedure	Screening ≤ 28 days from Baseline (First day drug administration)	Cycle 1				Cycles 2, 4, 6, 8	Cycles 3, 5, 7, 9	Discontinuation From Protocol Therapy	Follow-Up Phase
		Day 1	Day 8	Day 15	Day 22	Day 1	Day 1		Not indicated
Record prior medications, treatments	X								
Record prior anti-cancer therapies	X								
Physical examination, vital signs, weight	X	X ⁹				X	X	X	
ECOG performance status	X	X ⁹				X	X	X	
CT or MRI of the chest & abdomen / pelvis	X					X ⁷		X	
Chest x-ray ¹	X ¹					X ¹		X ¹	
Bone scan ²	X ²					X ²		X ²	
CT or MRI of the brain	X ³					X ³		X ³	
ECG	X							X	
Hematology	X	X ⁹		X		X	X	X	
Serum chemistry ⁴	X	X ⁹		X		X ⁴	X ⁴	X	
Pregnancy testing ⁵	X ⁶	X	X	X	X	X ⁶	X ⁶	X ⁶	
Register patient into RevAssist® program	X								
Baseline lesion assessment	X								
Dispense everolimus via IDS		X ¹⁰				X ¹⁰	X ¹⁰		
Prescribe lenalidomide via RevAssist® ¹⁰									
Response assessment ⁷						X ⁷		X	
Record adverse events ⁸			X		X	X	X	X ⁸	
Record concomitant therapies/procedures			X		X	X	X	X	
Obtain Follow-Up anti-cancer treatments									X
Obtain Follow-Up survival information									X
Obtain Archival Tissue Block	X								
Collect Blood Sample for Correlative Assay	X ¹¹	X ¹¹				X ¹¹		X ^{11,12}	
Fresh Tumor Biopsy ¹³	X ¹³					X ¹³			

* Variations of ± 3 days of the scheduled visit are permitted.

If Physical examination, vital signs, weight and ECOG performance status were done within 7 days of Day 1, they do not need to be repeated at Study Day 1.

An unscheduled visit can occur at any time during the study. Source must be maintained for these unscheduled visits. The date for the visit and any data generated must be recorded on the appropriate CRF. Source documents for these unscheduled visits must also be maintained.

¹ Not needed if Chest CT scan has been obtained.

² May repeat as clinically indicated if subject had previously positive bone scan or if symptoms suggest metastases.

³ If symptoms raise suspicion of CNS lesions.

⁴ To include Thyroid Stimulating Hormone (TSH) at Screening, every 16 weeks and at treatment discontinuation. T3 and T4 levels may be assessed as clinically indicated.

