10.2 Datasets to be analyzed

Demographics

Subject demographics including age, sex, race, ethnicity, height, weight, disease information, and medical conditions will be summarized by cohort using descriptive statistics.

Extent of Drug Exposure

The total number of doses of lenalidomide and everolimus (mg), and total number of treatment cycles delivered will be summarized by dose level using descriptive statistics.

Efficacy Endpoints

The secondary endpoint of the trial is response rate. The best overall response rate as defined by the proportion of subjects who have had a CR or PR will be summarized by dose level. Any subject treated in the expansion phase with overall response assessment of partial or complete response will have the response confirmed by repeat assessment no less than 4 weeks after the criteria for response are first met. The RR will be summarized by dose level using descriptive statistics along with a 95% confidence interval.

Pharmacokinetic Parameters

Serum concentration of study drug will be determined by a validated method according to assessment schedules. The pharmacokinetic parameters will be summarized using descriptive statistics.

The concentrations of everolimus, lenalidomide and their clinically significant metabolic product will be summarized by dose level using descriptive statistic. The mean concentration for each dose level will be plotted on scheduled sample time. The following pharmacokinetic parameters will be estimated and reported for each agent according to dose level.

$AUC_{0 \rightarrow t}$ Area under the concentration-time curve from the time of dosing to the time of the last observation; $AUC_{0 \rightarrow \infty}$ Area under the concentration-time curve from the time of dosing extrapolated to infinity; C_{max} Maximum serum concentration observed postdose; T_{max} Time point at which the C_{max} occurs; $t_{1/2}$ Elimination half-life, determined as $0.693/\lambda_z$.

Pharmacodynamic Correlates

The levels of mTOR pathway proteins, inflammatory cytokines and lymphocyte subsets at each specified time point will be reported in a descriptive manner for each dose schedule and analyzed by tumor type, when appropriate. Data will also be explored graphically. The PK and

pharmacodynamic data will be used to describe potential relationships between plasma levels of everolimus and or lenalidomide and changes in serum protein, toxicities, and tumor response.

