10.6 Sample size and power considerations

The sample size of up to 30 patients is required to establish the MTD and the RP2D based on the proposed modified Fibonacci dose escalation schema assuming that each dose cohort requires the maximum of 6 subjects. Up to 6 subjects will be enrolled at each dose level. If no DLTs occur, a total of 15 subjects will be needed to complete the dose escalation part of the study. To further characterize safety and efficacy, fifteen additional subjects will be enrolled at the MTD in an expansion cohort. In order to perform preliminary evaluation of anti-tumor activity, the sample size at the MTD or highest dose level cohort is determined by a power analysis. It is assumed that the subjects would have no response if they would not have received any therapy and that response rate for subjects in the MTD or highest dose level cohort would be 10%. Based on this assumption, a sample size of 15 subjects in the MTD cohort will provide more than 79% power in a one-sample exact binomial test at the significance level of 0.05. We anticipate accrual of 2-3 patients per month for the escalation phase and approximately 1-2 patients per month for the expansion phase, which is restricted to patients with clear cell renal cell carcinoma. At this accrual rate, we expect total accrual and study completion within 18-24 months.

A parallel expansion cohort of 9 patients with adenoidcystic carcinoma will also be evaluated. An objective response in at least 3 of 9 patients will be considered sufficient evidence to explore the benefit of this regimen in a larger phase II efficacy trial. The expected maximum overall sample size of 45 patients will still be maintained with the addition of this parallel cohort because only 21 of the maximum expected 30 patients were required in the dose escalation of the study.

11 Regulatory Considerations

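### Section 9.1 times the efficacy analysis by enrolment, about three weeks short of the last patient's second restaging, and no section says when the 3-of-9 rule is read

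*Combined protocol and SAP*

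**What the plan says.** - **Reporting date.** Section 9.1: "Data will be analyzed and reported within 3 months of enrolment of the last patient in the expansion cohort". It continues: "All subsequent data collected will be analyzed and reported in a follow-up clinical report". The second report has no date or trigger, and the text speaks of one expansion cohort.
- **Two expansion cohorts.** Section 10.6 plans 15 patients at the MTD and then adds: "A parallel expansion cohort of 9 patients with adenoidcystic carcinoma will also be evaluated". Three or more objective responses among those nine would support a larger phase II trial. The rule does not say whether responses must be confirmed or at which report they are counted.
- **Scan schedule.** The synopsis sets a 28-day cycle ("Lenalidomide once daily days 1-28 of a 28 day cycle"). Section 7: "Efficacy assessments are scheduled to occur after every 2 cycles of protocol therapy or approximately every 8 weeks". Under Section 2, "Variations of ± 3 days of the scheduled visit are permitted".
- **Confirmation.** Section 7: "All partial and complete responses will be confirmed with another efficacy assessment in no less than 4 weeks apart". Section 10.2 says that a responder in the expansion phase "will have the response confirmed by repeat assessment no less than 4 weeks after the criteria for response are first met". Section 7.1.3 makes confirmation a condition of PR or CR status, but allows unconfirmed responses to be reported as such where confirmation is not feasible. Footnote 7 of Section 2 points the other way: it asks for no separate confirmatory scan and relies on the regular restaging scans.

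**The concern.** The reporting date is counted from the last enrolment, not from the follow-up that a response assessment needs. The patients enrolled last may have had only one restaging when the data are analysed. Their responses would then be unconfirmed, and any that appear at the second restaging would be absent.

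The number of patients is small, but so is the threshold. With 3 of 9 as the rule, one unresolved patient can decide the answer. Two reports without a stated order of precedence could give two response rates and two answers on whether to go to phase II. Section 10.5 plans no interim efficacy analysis, so nothing there says how an early reading relates to the final one.

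**Working it through.** **The plan's own figure.** Section 10.6 gives more than 79% power for 15 patients, 0% against 10%. With one response enough to reject 0%, power = 1 − 0.9^15 = 0.794, which agrees. This assumes that a response in any of the 15 can be counted. With 14 countable it is 1 − 0.9^14 = 0.771; with 13, 1 − 0.9^13 = 0.746.

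**Timeline for the last patient.** Inputs: 28-day cycles (synopsis), restaging every 2 cycles (Section 7), a 4-week minimum to confirmation (Sections 7, 7.1.3, 10.2), and a deadline of 3 × 30.44 = 91.3 days (Section 9.1). I take first dose as the day of enrolment, which favours the plan.

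| Event | Day | Against Day 91.3 |
|---|---|---|
| First restaging | 2 × 28 = 56 | 35.3 days before |
| Earliest permitted confirmation (unscheduled scan) | 56 + 28 = 84 | 7.3 days before |
| Second restaging, the regular confirmation of a Day 56 response | 4 × 28 = 112 | 20.7 days after |
| Unscheduled confirmation of a Day 112 response | 112 + 28 = 140 | 48.7 days after |
| Third restaging, the regular confirmation of a Day 112 response | 6 × 28 = 168 | 76.7 days after |

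The ± 3-day window moves Day 112 to Day 109 at the earliest, which is still late. The second on-treatment correlative samples in Appendix D (Day 1 of cycle 5, so Day 4 × 28 + 1 = 113) also fall after the deadline for the last patient.

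**Patients short of Day 112 at the deadline.** Section 10.6 expects 1–2 expansion patients per month, a spacing of 30.4 or 15.2 days. Number short = 1 + whole part of (gap ÷ spacing).

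- Data cut on the deadline itself: gap 20.7 days. 20.7/30.4 gives 1 patient; 20.7/15.2 gives 2.
- Data cut 14 days earlier (assumption): gap 34.7 days. 34.7/30.4 gives 2; 34.7/15.2 gives 3.
- Data cut 28 days earlier (assumption): gap 48.7 days. 48.7/30.4 gives 2; 48.7/15.2 gives 4.

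**Worst-case effect on the 3-of-9 rule.** Suppose that 1 or 2 of the nine cannot yet count and are treated as non-responders. The chance of meeting the rule is P(X ≥ 3) for a binomial with n = 9, 8 or 7. The true response rates are assumptions.

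| True rate | 9 counted | 8 counted | 7 counted |
|---|---|---|---|
| 20% | 0.262 | 0.203 | 0.148 |
| 30% | 0.537 | 0.448 | 0.353 |
| 33% | 0.615 | 0.52 | 0.422 |

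**The case against.** A reader might infer that the last patients cannot reach a confirming scan in time, that the 3-of-9 rule is read too early, and that the response rate is biased low. The documents do not support any of the three in that form.

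- **Confirmation in time is possible.** The 4-week minimum permits a scan at Day 84, inside the limit. But no such scan is scheduled, and about 7 days remain for cleaning, analysis and reporting. The clock also starts at enrolment, and footnote 10 of Section 2 suggests prescribing lenalidomide 5 to 7 days before Day 1. If that follows enrolment, the margin nearly disappears.
- **Confirmation may not be required.** Under footnote 7 a Day 56 response could stand alone. That conflicts with Sections 7, 7.1.3 and 10.2, and even then a response first seen at Day 112 is missed, although Section 10.2 analyses best overall response.
- **The reading time is unspecified, not stated to be early.** Section 10.6 ties the rule to neither report, and Section 9.1 does promise a follow-up report. So the rule can be read on immature data; the plan does not say that it will be.
- **No section counts unconfirmed patients as failures or drops them.** Section 7.1.3 lets a response be reported as unconfirmed. Downward bias is one possible outcome, and the table for the 3-of-9 rule is a worst case.
- **Response is a secondary endpoint of a phase I trial.** MTD and safety are primary and DLT is assessed in cycle 1, so a prompt first report followed by a later one is a legitimate design. This stands, and it is why the early report should be kept for safety and MTD.

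The table in Section 2 places the imaging mark under the even-numbered cycles, in a column headed Day 1. Read literally, the second scan would fall on Day 3 × 28 + 1 = 85, also about 6 days before the limit. Section 7, footnotes 7 and 11 and Appendix D all put restaging after two completed cycles, so I use that.

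**Conclusion.** The concern holds in a limited form. The Section 9.1 deadline is too short for the protocol's own response schedule by about 3 weeks at the second restaging. The plan also leaves open what starts the clock (the 15-patient or the 9-patient cohort), what triggers the follow-up report, and which report decides the 3-of-9 rule. If the 15-patient cohort starts the clock, the 9-patient cohort could still be enrolling when the first report is due.

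The effect is confined to the last few patients: 1–2 on the stated accrual, or 2–4 if analysis takes 2–4 weeks. That accrual rate is given for an expansion described as restricted to clear cell renal cell carcinoma. No rate is given for adenoid cystic carcinoma, so applying it to the nine is an assumption. The fall from 62% to 52% or 42% further assumes a 33% true rate, that the unresolved patients all belong to the adenoid cystic cohort, and that they count as failures. The chronology rests on the documents; the size of any effect on the decision does not. This is worth correcting because the correction is cheap, but it does not undermine the primary objectives.

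**What to change.** Amend Sections 9.1 and 10.6 as follows.

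1. Keep the 3-month report for safety and MTD, and state which cohort's last enrolment starts its clock. Label any response shown in it as preliminary.
2. Define the efficacy cut-off as the date when every patient in both expansion cohorts has had the end-of-cycle-4 restaging or has progressed, died or withdrawn. For a response first seen at that scan, extend the cut-off to the next regular restaging.
3. Report the response rate and apply the 3-of-9 rule once, at that cut-off, in the follow-up report already planned, with 3 months for analysis.
4. Reconcile footnote 7 of Section 2 with Sections 7, 7.1.3 and 10.2, and state in Section 10.6 whether the 3-of-9 rule uses confirmed responses.

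The cost is time. With the same 3 months for analysis, the efficacy report moves back by the length of the cut-off: 112/30.44 = 3.7 months, or 168/30.44 = 5.5 months if a response first seen at Day 112 must be confirmed. No extra patients are needed, and no extra scans if confirmation uses the regular restaging. Taking cycle 4 as the end point is a choice; another would do if it is fixed in advance.
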